## 12.4. Deaths and Serious Adverse Events

A listing by subject of all deaths will be produced. Primary cause of death, subreason of death, date of death and time from last dose will be listed for each subject who died.

All SAEs will be tabulated based on the number and percentage of subjects by frequency and maximum grade. SAEs are included in the listing of all adverse events. A supportive listing with all SAEs will be generated including fatal SAEs.

In addition, summary table of serious adverse events for all subjects by system organ class and preferred term including drug-related status and fatal status will be generated.

### 12.5. Adverse Events Leading to Discontinuation of Study Treatment and/or Withdrawal from the Study and Other Significant Adverse Events

The following categories of AEs will be listed separately with subject level details:

- AEs Leading to Discontinuation of Study Treatment or Withdrawal from the Study
- AEs leading to Dose Interruptions or Dose Delay or Dose Reductions

## 12.6. Pregnancies

While pregnancy itself is not considered to be an AE or SAE, any pregnancy complication or elective termination of a pregnancy for medical reasons will be recorded as an AE or SAE as described in the protocol. If subjects and subjects' partner become pregnant while on the study, the information will be included in the narratives and no separate table or listing will be produced.

# 12.7. Clinical Laboratory Evaluations

The assessment of laboratory toxicities will examine the following laboratory tests:

Hematology				
Platelet Count		RBC Indices:	Automated WBC Differential:	
Red blood cell (RBC) Count		Mean corpuscular volume (MCV)	Neutrophils	
White blood cell (WBC) Count (absolute)		Mean corpuscular hemoglobin (MCH)	Lymphocytes	
Reticulocyte Count		Mean corpuscular hemoglobin concentration (MCHC)	Monocyte	es
Hemoglobin			Eosinoph	ils
Hematocrit			Basophils	6
Clinical Chemistry				
Blood urea nitrogen (BUN) or urea	Potassium	AST		Total and direct bilirubin
Creatinine	Chloride	ALT		Uric Acid
Glucose, fasting	Total carbon dioxide (CO 2 )	Gamma glutamyl tra (GGT)	nsferase	Albumin
Sodium	Calcium	Alkaline phosphatas	е	Total Protein
Magnesium	Phosphate			
Routine Urinalysis				
Specific gravity				
pH, glucose, protein	i, blood and keto	ones by dipstick		
Microscopic examinat	tion (if blood or pr	otein is abnormal)		
Other tests				
PT, INR, PTT				
Testosterone (male si	• • /			
Luteinizing Hormone		• •		
Follicle stimulating ho	rmone (FSH) and	l estradiol (as needed ir	n women of	non-child bearing potential only)

Summaries of change from baseline for clinical chemistry and haematology data by maximum toxicity grade will be provided by scheduled visits for all the lab tests that are gradable by CTCAE v4.0. Number and percentage of subjects with any post-baseline

grade increase or any maximum increase to grade 3 or grade 4 will be displayed in the table. Data collected in unscheduled visits will be included in the summary of worst case on therapy category. Data with missing baseline grade will be excluded from the summary.

Another set of tables of summary of change from baseline for lab data with respect to normal range will be generated. Decreases to low, changes to normal or no changes from baseline, and increases to high will be summarized at each scheduled visit as well as for the worst case post-baseline. If a subject has a decrease to low and an increase to high during the same time interval, then the subject is counted in both the "Decrease to Low" categories and the "Increase to High" categories. In addition, the summary will include worst case changes from baseline with respect to normal range including non-scheduled visits.

Laboratory data of clinical chemistry, haematology, urinalysis, coagulation and other data will be listed for all subjects, respectively.

A supporting listing of subjects with Grade 3 or higher toxicities will be provided separately for each of above lab categories. All laboratory data will be reported under standard units.

### 12.7.1. Analyses of Liver Function Tests

Hepatobiliary laboratory abnormalities will be summarized. Liver function tests will be listed for all subjects with Grade 3 or greater toxicities in any liver function test. A separate listing will be provided for all subjects with possible Hy's law event, which is defined as ALT  $\geq$ 3ULN and bilirubin  $\geq$  2ULN.

### 12.8. Other Safety Measures

Unless otherwise specified, the denominator in percentage calculation at each scheduled visit will be based on the number of subjects with non-missing value at each particular visit.

Values of vital signs as well as the change from baseline will be summarized by scheduled visit using mean, median, standard deviation, minimum and maximum.

In addition vital sign values will be categorized as follows:

- Systolic BP (mmHg): Grade 0 (<120), Grade 1 (120-139), Grade 2 (140-159) and Grade 3 (≥160), and Decrease to <90.
- Diastolic BP (mmHg): Grade 0 (<80), Grade 1 (80-89), Grade 2 (90-99), and Grade 3 (≥100), and Decrease to <=35.
- Heart rate (beats/min): <60, 60-100, and >100
- Temperature (°C): <35, 36-37, ≥38

Summaries of increase in vital signs and decreases in systolic BP from the baseline with respect to the categories defined above, and details in Section 9.4.3, will be performed.

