2. OBJECTIVE(S) AND ENDPOINT(S)

2.1. Part 1: Dose Escalation and PK-PD Cohorts

Objective	Endpoint
Primary	

 To determine the safety and tolerability of GSK2849330 in subjects with advanced HER3-positive solid tumors. 	
 AEs, serious adverse events (SAEs), DLTs, and changes in laboratory values, electrocardiograms (ECGs), and vital signs.
Secondary	

 To characterize the PK of GSK2849330 following IV administration. To evaluate preliminary evidence of target engagement and PD effects of GSK2849330 To determine the recommended dose regimen(s) of GSK2849330 for further exploration in Part 2. To evaluate the immunogenicity of GSK2849330 following IV administration. 	
 PK parameter values for GSK2849330. Total and phospho-HER3 from tumor tissue Safety, tolerability, PK, and available PD data. Antibodies to GSK2849330 assessed in serum
Exploratory	

 To further evaluate preliminary evidence of target engagement and PD effects of GSK2849330. To explore relationships between GSK2849330 PK, markers of target engagement, and /or PD markers. To explore preliminary clinical tumor outcomes after treatment with GSK2849330. 	
 Pre- and post- treatment biomarkers (cells, proteins, ribonucleic acid [RNA] and/or deoxyribonucleic acid [DNA]) from circulation, skin, and/or tumor tissue. GSK2849330 concentration-time profile and PK parameters, target engagement and PD markers in circulation, skin, and/or tumor Preliminary evidence of clinical benefit as assessed by overall response rate (ORR), tumor markers, and other measures of clinical benefit
Pharmacogenetic (PGx) Exploratory	

 To investigate the relationship between genetic variants in candidate genes and safety, tolerability, PK, PD, and/or efficacy of GSK2849330. 	
 Genetic variations in selected candidate genes, such as the FCγ receptor family, safety, tolerability, PK, PD, and/or efficacy endpoints.

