#### 9.4.3. Vital Signs

To identify heart rate values of potential clinical importance, NCI-CTCAE v4.0 will be used to assign categories that align with the grades for 'Sinus bradycardia', 'Sinus tachycardia', 'Supraventricular tachycardia', and 'Ventricular tachycardia'.

The following criteria will be used to flag vital sign values that are values of potential clinical importance:

Vital Sign Parameter	Potential Clinical Importance (PCI) Range	Unit
Decrease from baseline Heart Rate	Decrease to <60	bpm
Increase from baseline Heart Rate	Increase to >100	bpm

To identify blood pressure values of potential clinical importance, NCI-CTCAE v4.0 will be used to assign categories that align with the grades for 'Hypertension'.

Vital Sign Parameter	Potential Clinical Importance (PCI) Range	Unit
Increase from baseline	$\geq 120 \text{ to } < 140 \text{ (Grade 1)}$	mmHg
Systolic Blood Pressure	$\geq$ 140 to <160 (Grade 2)	
	≥160 (Grade 3)	
Increase from baseline	≥80 to <90 (Grade 1)	mmHg
Diastolic Blood Pressure	$\geq$ 90 to <100 (Grade 2)	
	≥100 (Grade 3)	

To identify temperature values of potential clinical importance, NCI-CTCAE v4.0 will be used to assign categories that align with the grades for 'Hypothermia' and 'Fever'.

Vital Sign Parameter	Potential Clinical Importance (PCI) Range	Unit
Increase from baseline	Increase to ≥38	Degrees
temperature		С
Decrease from baseline	Decrease to ≤35	Degrees
Diastolic Blood Pressure		С

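### SAP 9.4.3 labels the 35 °C limit as diastolic blood pressure, 12.8 has 35 on the diastolic line, and the 12.8 temperature bands leave gaps

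*SAP*

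**What the plan says.** Protocol 2.1 names among the primary endpoints of Part 1 AEs, SAEs, DLTs "and changes in laboratory values, electrocardiograms (ECGs), and vital signs"; Protocol 2.2 does the same for Part 2. Protocol 13.7.2.4 says that vital signs will be summarised against criteria of potential clinical importance fixed in advance, and leaves the detail to the reporting and analysis plan. Those criteria are in two places in the SAP.

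- **SAP 9.4.3.** The blood pressure table, tied to the CTCAE grades for hypertension, has increase rows only. A separate table follows, introduced by "To identify temperature values of potential clinical importance" and tied to hypothermia and fever. Its high row reads "Increase to ≥38" and is labelled temperature. Its low row reads "Decrease to ≤35", has degrees C as its unit, and is labelled as a decrease in diastolic blood pressure.
- **SAP 12.8.** The systolic line gives four grades "and Decrease to <90". The diastolic line, in mmHg, gives four grades "and Decrease to <=35". The temperature line reads "Temperature (°C): <35, 36-37, ≥38". The closing sentence plans "Summaries of increase in vital signs and decreases in systolic BP from the baseline with respect to the categories defined above" and refers to 9.4.3 for details.

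The planned displays are Table 11.32 (heart rate and temperature, worst-case change), Table 11.33 (blood pressure, worst-case change) and a listing of all vital signs.

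**The concern.** The number 35 has a plain meaning as a body temperature in °C, and 9.4.3 places it in a temperature table with that unit. The label there is for a different measurement, and 12.8 has the same number as a limit in mmHg. A programmer who follows the text has no row in 9.4.3 that is named as low temperature, and has a low-diastolic category whose source cannot be found in the blood pressure criteria.

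Separately, the 12.8 temperature line is written as a set of bands, but the bands do not meet. Section 12.8 takes as its percentage denominator the subjects with a non-missing value at the visit. If the bands are tabulated, a subject whose temperature falls between two of them is counted in the denominator and in no category.

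At stake is whether the criteria promised in Protocol 13.7.2.4 can be programmed as written, for one component of the primary safety endpoint.

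**Working it through.** There is no sample size, error rate or planned figure to reproduce. The check sets the two SAP sections side by side and then tests whether the bands cover the scale.

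**Step 1: the limits compared.**

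| Item | SAP 9.4.3 | SAP 12.8 | Agree? |
|---|---|---|---|
| High temperature | 38 or above | 38 or above | Yes |
| Low temperature | 35 or below, degrees C, under a diastolic label | below 35 | No: label, and the value 35.0 |
| Heart rate | below 60, above 100 | below 60, 60 to 100, above 100 | Yes |
| Systolic and diastolic grades 1 to 3 | increase rows | same cut-points | Yes |
| Systolic low | no row | below 90 mmHg | In 12.8 only, but the 12.8 summary sentence names systolic decreases |
| Diastolic low | no row in the blood pressure table | 35 or below, mmHg | In 12.8 only, and the summary sentence does not name diastolic decreases |

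The systolic low limit is also missing from the 9.4.3 blood pressure table, so absence from that table does not by itself show an error. The diastolic limit differs in two ways: no sentence plans a summary that would use it, and its value matches the mislabelled temperature row. That the number passed from one section to the other is the likeliest explanation, but it is an inference that neither document states.

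**Step 2: temperature bands as written.** Take values from 34.0 to 40.0 °C in steps of 0.1, which gives (40.0 − 34.0)/0.1 + 1 = 61 values. Assign each to below 35, 36 to 37, or 38 and above.

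- No band: 35.0 to 35.9 (10 values) and 37.1 to 37.9 (9 values). 10 + 9 = 19 of 61.

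The documents do not give the recording precision, so one decimal place is an assumption. Other readings:

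| Reading of the bands | Values in no band |
|---|---|
| One decimal place, as written | 35.0–35.9 and 37.1–37.9 |
| Whole degrees only | 35 |
| Rounded to whole degrees first | 34.5–35.4 |
| Middle band read as 36.0–37.9 | 35.0–35.9 |

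A gap at the low end remains under every reading.

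**Step 3: conflict between sections.** The limits 35 or below and below 35 differ on the grid at one value, 35.0. Under 9.4.3 (with the label corrected) that value is of potential clinical importance; under 12.8 it has no category.

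**Step 4: the diastolic item.** Every diastolic value of 35 mmHg or below is also below 80, hence Grade 0. The item therefore overlaps the grades and does not extend them.

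**Step 5: bands built from the SAP's own limits.** With 35 or below, above 35 to below 38, and 38 or above, 0 of 61 values are unclassified.

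**The case against.** The strongest reply is that these are drafting slips with little reach, and much of it stands.

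- A reader might infer that the vital-sign flags in general are wrong. They are not. The fever, heart rate, systolic and blood-pressure-increase limits are sound, and the temperature gaps lie between the flag limits. They change category counts, and touch a flag only at 35.0 (or from 34.5 to 35.4 if values are rounded first).
- A reader might infer that low diastolic pressure will be flagged only at 35 mmHg or below. The 12.8 summary sentence names decreases for systolic pressure alone, so it is unclear whether the diastolic item would be tabulated at all, and the plan shows no other diastolic limit that has been lost.
- A reader might infer that hypothermia has no criterion. The row exists; its position and unit show its purpose, and only the label is wrong. Section 12.8 also has a low band.
- A reader might infer that published percentages will not sum to 100%. That is possible if the 12.8 bands become table rows, but Table 11.32 uses a standard shell that the SAP does not reproduce, and the 9.4.3 criteria are one-sided flags for which an unflagged middle is normal.
- A reader might infer that the infusion-reaction analysis is affected. SAP 12.3 identifies those reactions from adverse event terms, not from vital-sign bands.

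The primary endpoint also has other cover. Section 12.8 summarises values and changes by visit as continuous data, all vital signs are listed, and Protocol 8.3 requires abnormalities judged clinically significant to be recorded as adverse events.

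The reply does not remove the errors. The wrong label, the unsupported limit and the open bands are instructions in the current SAP, and the diastolic limit is in the running text of 12.8, so broken table extraction cannot explain it.

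**Conclusion.** The point holds in a limited form. One row in SAP 9.4.3 has the wrong label, one limit on the diastolic line of 12.8 has no support elsewhere in the plan, and the 12.8 temperature bands are neither contiguous nor consistent with 9.4.3 at 35.0 °C. The effect is confined to the low-temperature flag, any low-diastolic category, and the temperature category counts. The continuous summaries, the listings, the infusion-reaction analysis and every other vital-sign limit are unaffected. SAP section 7 plans no formal comparisons, and no test, sample size or escalation rule uses these limits.

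The size of the gap rests on the assumption of readings to one decimal place. That a gap exists does not. The figure of 19 of 61 describes the scale and is not an estimate of how many subjects would fall in the gaps. This is a minor correction, worth making because these lines are the criteria that Protocol 13.7.2.4 promises.

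**What to change.** 1. In SAP 9.4.3, relabel the low row of the temperature table as a decrease in temperature.
2. In SAP 12.8, remove the 35 from the diastolic line. If a diastolic limit in mmHg was intended, the sponsor should reconcile 9.4.3 and 12.8, and state whether diastolic decreases are to be summarised.
3. In SAP 12.8, make the temperature bands contiguous, with a single low limit that matches 9.4.3. One set built from the SAP's own limits is 35 or below, above 35 to below 38, and 38 or above. Whether 35.0 itself counts as low is for the sponsor to settle, and 9.4.3 already names CTCAE v4.0 as the reference.

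The cost is three lines of the SAP and the matching program specifications. No additional data are needed.

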#### **Performance Status**

ECOG performance status will be summarized at baseline and each post-baseline scheduled visit. Summaries will use frequency and percentage of subjects at each planned assessment time. A summary of change from baseline by scheduled visits will be performed, as well as the worst case post-baseline and the best case post-baseline changes during the study (improved, no change, deteriorated).

A supporting listing will also be provided.

#### ECG

As per the protocol, all ECGs will be single assessments unless clinically significant abnormality is observed, in which case repeat ECG twice more, for a total of 3 ECGs within approximately 5-15 minutes. Manual calculation for all 3 ECGs should be done using Fridericia's formula (QTcF=QT/RR1/3) in view of the complex relationship between QT and RR.

Any clinical decisions should be based on the average of all three ECGs.

The following parameters will be derived if applicable, where they are derived to the same number of decimal places as the raw data.

Variable	Description	Algorithm
RR	R RR interval	
 
If QTcB is machine read and QTcF is not provided, then: RR = [(QT/QTcB)^(2)]*1000
 
If QTcF is machine read and QTcB is not provided, then: RR = [(QT/QTcF)^(3)]*1000
 
If ECGs are manually read, the RR value preceding the measured QT
 

		interval should be a collected value Do Not Derive.
QTcB	QTc interval, using Bazett's correction	
 
If not provided in dataset, derive:
 
QTcB = QT / ((RR/1000)^1/2), where RR is in msec
 

QTcF	QTc interval, using Fredericia's correction	
 
If not provided in dataset, derive:
 
QTcF = QT / ((RR/1000)^1/3), where RR is in msec
 

A summary of the number and percentage of subjects who had normal and abnormal (clinically significant and not clinically significant) ECG findings will be displayed by part, dose group, and scheduled visits as well as for the worst case post-baseline. See Section 9.4.2 for details.

In addition, ECG interval values will be also be summarized.

Listings of abnormal ECG findings and a listing of ECG values will be provided.

A figure plotting the baseline QTc and the worst-case post-baseline values will be produced. The figure will have reference lines at 450 and 500 msec for both the ordinate and the abscissa axes. There will be diagonal reference lines at equality (i.e. a 45 degree line), at equality plus 30 msec, and at equality plus 60 msec.

### LVEF

Absolute change from baseline in LVEF will be summarized at each scheduled assessment time and in the worst case post-baseline. Only the post-baseline assessments that used the same method (ECHO or MUGA) as the baseline assessments will be used to derive the change from baseline. The change from baseline will be categorized as follows:

- Any increase
- No change
- Any decrease:
- >0-<10 decrease
- 10-19 decrease
- >=20 decrease
- $\geq 10\%$  decrease and  $\geq LLN$
- $\geq 10\%$  decrease and < LLN
- $\geq 20\%$  decrease and  $\geq LLN$
- $\geq 20\%$  decrease and < LLN

LVEF results will also be listed with subject level details including absolute change from baseline.

#### **Liver Events**

For any liver events that occur during the study, the liver event information for RUCUM score will be summarized, including whether the subject was age 55 or over, whether the subject became pregnant, liver imaging normal or not, a biopsy was taken or not, whether there was fasting or significant dietary change, whether the subject took any unconventional medications, timing when the event occurs (while on treatment or after stopping treatment) and summary statistics for time from first dose to start of liver event and time from last dose to start of liver event. If the number of events does not support a summary, then only listings will be produced.

For subjects with multiple events, the first event will be used for the summary tables. All events with subject level details will be displayed in a supporting listing.

# 13. PHARMACOKINETIC ANALYSES

The reconciliation of the PK Case Report Form (CRF) and SMS2000 data will be performed by, or under the direct auspices of, Data Sciences - Oncology, GlaxoSmithKline.

The merge of PK concentration data and CRF data to generate a dataset with actual blood sampling times, actual time relative to dosing, and PK concentrations will be performed after DBF by, or under the direct auspices of Clinical Statistics, Oncology Quantitative Sciences (Programmer), GlaxoSmithKline.

Derivation of pharmacokinetic parameters will be performed by, or under the direct auspices of, Clinical Pharmacology Modeling and Simulation (CPMS), GlaxoSmithKline.

Statistical analysis of pharmacokinetic parameters will be performed by, or under the direct auspices of, Clinical Statistics Oncology Quantitative Sciences (Statistician), GlaxoSmithKline.

Unless otherwise stated, all tables, figures and listings in this section will be based on the Pharmacokinetic, or PK Parameter population, and all summaries, figures will use treatment labels as specified in Section 7 and PK concentration listing will be presented by part and dose level.

The lists of displays for PK, including population to use for each display, are shown in Section 19 of the RAP.

## 13.1. Drug Concentration Measures

Concentrations of GSK2849330 in the collected PK plasma samples will be determined using the currently validated and approved analytical ELISA assay. The generated concentration data will be reported in SMS2000. Raw data will be stored in the GLP Archives, GSK. The analysis and reporting of the PK drug concentrations of GSK2849330 will be performed under the management of Bioanalysis, Immunogenicity and Biomarkers (BIB), In Vitro/In Vivo Translation, GSK.

All PK concentration listing displays will be based on PK Concentration Population, and PK concentration summary displays (tables/figures) will be based on PK parameter population.

Concentrations of GSK2849330 in plasma will be listed by part, original dose group and nominal time and summarised by dose group and nominal time. Standard summary statistics will be calculated (i.e. mean, standard deviation, median, minimum and maximum). Refer to the PK Guidance document GUI\_51487, "Non-Compartmental Analysis of Pharmacokinetic Data", for more information regarding the handling of plasma concentrations below the assay's lower limit of quantification (NQ).

Individual GSK2849330 concentration-time profiles and median/mean profiles by treatment dose group will be plotted using actual elapsed time for individual plots and

nominal time for median/mean profiles for each study part. Each of the figures will contain one plot on the untransformed scale (i.e. a linear plot) and one plot on the log transformed scale (i.e. log-linear plot). See Section 19 Pharmacokinetic Source Figures and Tables for details.

Any concentration data excluded from the derivation of PK parameters by CPMS should be omitted from any figures and summaries, and flagged with an asterisk in the relevant data listings, with a footnote to indicate that these values have been omitted from subsequent analyses.

